#### 10. Describe the means of analyzing the data and evaluating the results.

- *State the anticipated methods to be used for analysis and interpretation of the data.*
- *The methods must compliment the design of the study and the nature of the data which is being collected.*

Primary outcome measures for testing hypotheses will be walking speed measured during 10m walk trials and foot-to-floor clearance as measured by vertical displacement of marker placed over the first metatarsal using our 16-camera VICON motion analysis system. Force sensing resistors (FSRs) will be used to detect any toe dragging as a result of insufficient foot clearance. Secondary measures will be peak hip, knee and ankle flexion during swing, hip-knee coordination changes, knee flexion during stance and in pre-swing, step length symmetry and 6min walking distance.

The within subject experimental design will be used because it requires fewer subjects with more statistical power while reducing the potential for systemic error or selection bias to test the effect of CV on walking. While practice and carryover effects are major disadvantages of this study design, proper precautions including rest periods between tests and randomization of testing order for treatment group will be instituted to minimize them†. In addition to comparison between treatment and control groups, subjects receiving CV can also serve as their own controls by first comparing volitional gait at baseline (VGB) with any gait correction with the CV approximating desired normal muscle activity (CVN). Next the volitional gait *post*- 12 sessions of training with vibration (VGP) will be compared to volitional gait at baseline (VGB). Thus, any improvements at baseline with CVN compared to volitional gait (VGB) can be attributed to short term effects of vibration. Improvements in volitional gait *post* training with vibration (VGP) compared to baseline gait (VGB) will be attributed to long term effects of vibration. The control group subjects will be evaluated at baseline (VGB) and after gait training (VGP) and compared to the intervention group to identify trends and further explore the potential effects of CV. While this study design has limited generalizability due to the inhomogeneity of the selected population, it can be quite useful for developing and refining CV intervention.

A one-way repeated measures ANOVA will be used to test for significant difference between means to test Hypotheses 1 and 2. The Tukey honestly significant difference multiple comparison test will be used between each pair of mean walking speeds, foot-to-floor clearance and maximum joint angles to determine 95% ( $p < 0.05$ ) confidence intervals for

statistically significant differences between conditions (CVN-VGB, CVN-VGP, VGP-VGB) and between groups to identify trends across all subjects.

† Greenwald AG. With-in subject design: to use or not to use? *Psychological Bulletin*, 83(2):314-320, 1976.

**11. Provide a BRIEF DESCRIPTION of how the estimated number of study subjects needed for this research was determined**

- *If this is a quantitative study provide the method of determining sample size estimates.*
- *If multiple studies are planned provide a power analysis or justification for each one.*

A statistical power of 90% was used to determine the number of trials with VICON motion analysis system required for the testing and comparison of temporal and spatial gait parameters. The results indicated a requirement of 30 strides of data or roughly 6 trials (approximately 5 strides per trial) for each condition (volitional or CV). Because this is a two year feasibility study to determine the effect size a small sample of 6 subjects were chosen for intervention with six controls to obtain preliminary data for calculating statistical power for the number of subjects required in a larger study to determine the effect of vibration on improving gait in MS.

**12. The research involves the following procedures conducted by and for what purpose:**

| PROCEDURE   | PERFORMED BY:                       |                                    | PROCEDURE IS:            |                                     |
|---|-------------------------------------|------------------------------------|--------------------------|-------------------------------------|
|   | Research Staff                      | LSCDVAMC Clinical or Support Staff | Standard of Care*        | For Research Purposes Only**        |
| Audiotaping / Videotaping
Attach VA Form 10-3203 REQUIRED ONLY FOR IN-PATIENT AND OUT-PATIENT SUBJECTS |  |            |  |  |
| Biopsy   |             |            |  |             |
| Blood collection   |             |            |  |             |
| Chart review – prospective   |             |            |  |             |
| Chart review – retrospective   |  |            |  |  |
| Review of existing data ( ex: registry, Database , etc.)   |             |            |  |             |
| X-ray or Ionizing radiation exposure   |             |            |  |             |
| Clinical Tests   |             |            |  |             |
| Device implantation  |             |            |  |             |
| Drug administration  |             |            |  |             |

| PROCEDURE   | PERFORMED BY:                       |                                     | PROCEDURE IS:            |                                     |
|---|-------------------------------------|-------------------------------------|--------------------------|-------------------------------------|
|   | Research Staff                      | LSCDVAMC Clinical or Support Staff  | Standard of Care*        | For Research Purposes Only**        |
| EEG, EKG , ECG...etc  |             |             |  |             |
| Gene therapy, Genetic analysis  |             |             |  |             |
| Pregnancy/Breastfeeding Screening   |             |  |  |  |
| Interview, Questionnaire, Diary, Survey (please attach)                     |             |             |  |             |
| Stool collection, Urine collection, or any Non-surgical Specimen collection |             |             |  |             |
| Surgical procedure or Specimen removal during surgery                       |             |             |  |             |
| Tissue banking (complete Section 12)  |             |             |  |             |
| Use of pre-existing tissues/specimens                                       |             |             |  |             |
| Other (list): EMG and leg muscle vibration                                  |  |             |  |  |

- \*Standard of care procedures are procedures performed in the course of normal medical care.
- \*\*Research Procedures are performed for the purposes of this research alone.

**13. Please describe the research design and all study related procedures.**

- Describe **ALL PROCEDURES ASSOCIATED WITH THIS RESEARCH**. This includes standard of care and research procedures.
- For complex studies please include diagrams and tables. Be sure to describe when each procedure will be performed. Be sure to provide information for **each cohort, including normal controls**.

**Recruitment and baseline evaluation**

Potential subjects will be identified via chart review or through referral and asked if they would be willing to participate in the study. If agreeing, they would undergo the consent process. Twelve subjects with gait disorders from MS will be recruited for participation in this study, with six subjects assigned to undergo CV gait training and six to control group for gait training without vibration. Subjects will be randomly assigned to either treatment or control group and matched by functional walking category based on speed for data analysis†. After signing the consent form agreeing to participate in the study and meeting inclusion/exclusion criteria, subjects will undergo baseline evaluation. This will include walking speed and distance and using VICON system for temporal and spatial parameters, kinematics and kinetics of gait and EMG activity during volitional gait at their preferred walking speed.

Retro-reflective markers will be placed on the bony landmarks and surface EMG electrodes over target muscles while the subject walks along the 10m walkway instrumented with force platforms. Standard analysis software provided with VICON system will be used to track markers in 3D and calculate all gait parameters so they can be correlated with muscle activity. The baseline evaluation will be done with and without vibration on treatment group and without vibration on control group. Data will be collected during 6 walking trials of at least 5 steps per trial (approximately 30 steps) within the visual field of the VICON motion analysis system under each condition. Sufficient resting time will be provided between trials to complete the assessment. Subjects will be encouraged to use their walking aid while a trained physical therapist provides standby guard during walking for their safety.

[figure not shown]

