### Gait evaluation after gait training

After twelve 2 hour sessions of gait practice with cyclical vibration emulating normal muscle activity of lower extremities, baseline speed and distance trials and VICON gait assessment with and without vibration will be repeated to test hypotheses. The primary outcome measures for testing hypotheses will be walking speed and foot-to-floor clearance as measured by vertical

Vibratory stimulation system with inserts showing size and mounting of vibrators over TFL- tensor fasciae latae, RF- rectus femoris, BF- biceps femoris, and TA- tibialis anterior (VSCU-Vibratory Stimulation Control Unit).

displacement of marker placed over the first metatarsal. Force sensing resistors (FSRs) will be used to detect any toe dragging as a result of insufficient foot clearance. Secondary measures will be peak hip, knee and ankle flexion during swing, hip-knee coordination changes, knee flexion during stance and in pre-swing and step length symmetry.

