**14. Will the research involve the following?**

N/A **Chart/Data Review**

**Placebo Group**  No  Yes (*describe*):

**Other Control Group**  No  Yes (*describe*): Will be individuals with gait deficits from MS who will undergo the same gait training as treatment group but without cyclical vibration as described under #13 "research design and all study related procedures".

**Randomization**  No  Yes (*describe*): Subjects will be randomly assigned to either treatment or control group using a coin toss.

**Deception**  No  Yes (*describe*):

**15. Does the research involve the use and/or disclosure of Individually Identifiable Health Information in any form or medium?**

No  Yes **If yes, complete the required HIPAA Waiver/Authorization forms.**

**16. Does the study include the administration of a study agent that does not require FDA approval and does not require an IND (e.g. vitamins, food supplements, isotope tracers, alternative medicines, etc.)?**

No  Yes *-provide a detailed description of the procedures used to assure patient safety:*

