**Exclusion criteria:**

- Presence of demand pacemakers.
- Uncontrolled, functionally limiting edema of the affected limb/s.
- Uncontrolled seizures/epilepsy.
- Severe untreated depression affecting ability to participate in research.
- Botulin toxin treatment injected into the lower extremities within 12 months.
- Peripheral neuropathy in lower extremities.
- Respiratory disease severely limiting ability to walk.
- Uncontrolled chronic pain that limits short distance walking.
- Cardiac arrhythmias with associated hemodynamic instability contraindicating walking.
- Lower extremity injuries that limit range of motion or function required for stepping.
- Women during pregnancy.
- Patients with a relapse in the 3 months prior to presentation for study evaluation.

N/A Chart/data review

31. By role, (PI, Coordinator, etc.) who will assess for eligibility and how will this be accomplished?

PI and study staff will assess clinical eligibility and physical therapist will assess functional eligibility. The clinical eligibility will be assessed through review of medical history. Functional eligibility will be determined through manual muscle testing of strength and tone and standard clinical 10 m and 6 minute walking tests.

**32. Are any subjects excluded on the basis of race, ethnic group, understanding of English, socioeconomic status, education, gender, or pregnancy?**

- *Note: It is appropriate to indicate that you do not anticipate encountering potential subjects who do not speak English based on the population to be studied*

No       **Yes - (provide justification):** Understanding English because the subjects must be able to follow instructions during 12 sessions of therapy. Pregnant women will be excluded because the effects of cyclical vibration on fetus are not known.

N/A Chart/data review

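### Matching by walking-speed category for analysis is undefined, absent from both analysis sections, and a weaker use of baseline than adjusting for the measured value

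*Protocol*

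**What the plan says.** Protocol Section 3, item 13 (Recruitment and baseline evaluation) plans twelve subjects, "with six subjects assigned to undergo CV gait training and six to control group for gait training without vibration". It then says that they are randomly assigned and "matched by functional walking category based on speed for data analysis". The footnote on that sentence cites a paper titled "Classification of walking handicap in the stroke population". Item 14 gives the allocation method: "Subjects will be randomly assigned to either treatment or control group using a coin toss". It describes no stratification, blocking or pairing.

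Item 10 names the outcomes: "Primary outcome measures for testing hypotheses will be walking speed measured during 10m walk trials and foot-to-floor clearance". Both are measured at baseline. Item 10 plans a one-way repeated measures ANOVA with Tukey comparisons between conditions and between groups. The SAP plans a two-way ANOVA without naming its factors. Neither includes a matching factor or a baseline covariate. The documents do not give the number of walking categories, their cut-points, the matching ratio, or what happens to a subject without a partner.

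**The concern.** A coin toss that takes no account of walking ability will not, except by luck, give two small arms with the same number of subjects in each walking category. A promise to match afterwards may therefore be one that cannot be kept for everyone. The matching variable is also a banded form of walking speed, a primary outcome that is measured continuously at baseline. Two subjects can share a category and differ by its full width, or sit either side of a boundary and hardly differ.

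What is at stake is the comparison of vibration training with training alone. Depending on what matching means, that comparison either loses some of its 12 subjects or keeps part of a chance baseline imbalance. Since item 11 says the study is meant to supply data for sizing a larger trial, it is worth stating how the arms will be compared.

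**Working it through.** **Inputs from the documents.** Six subjects per arm (items 11 and 13), coin-toss allocation (item 14), and matching on a speed-based category (item 13). The sample size has no subject-level calculation to reproduce; item 11 says "a small sample of 6 subjects were chosen for intervention with six controls" and gives feasibility as the reason.

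**Assumptions, because the documents are silent.** K = 2, 3 or 4 categories, equally likely unless stated; matching read first as one-to-one within category, then as looser grouping.

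**1. Can all six pairs be formed?** With arms of six, complete matching needs identical category counts in both arms. Its probability is the sum of squared multinomial(6, p) probabilities:

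| K | Calculation | Probability |
|---|---|---|
| 2 | 924/4096 | 22.6% |
| 3 | 35169/531441 | 6.6% |
| 4 | 387136/16777216 | 2.3% |

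Uneven categories make matching easier: 42% for a 90/10 split, 17% for 80/10/10, and 7% for 70/10/10/10.

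**2. How many have no partner?** The number of pairs is the sum over categories of the smaller arm count. Its mean with six per arm is 4.65, 4.10 and 3.69 for K = 2, 3 and 4. Unmatched subjects = 12 − 2 × pairs, giving 2.7, 3.8 and 4.6.

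**3. Independent coin tosses.** A 6:6 split has probability C(12,6)/2^12 = 924/4096 = 22.6%. Multiplying by step 1 gives complete matching in about 5.1%, 1.5% and 0.5% of trials. By simulation, mean unmatched subjects are 3.9, 4.7 and 5.4. Over all the category splits tried, at least one subject is unmatched in 91% of trials or more.

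**4. Cost of dropping subjects.** Going from 12 subjects to 8 multiplies the standard error by √(12/8) = 1.22.

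**5. If nobody is dropped, how coarse is the category?** For a normally distributed baseline cut into K equal-probability bands with band means m_j (in SD units), the share of variance kept is R² = mean(m_j²): 0.637, 0.793 and 0.861 for K = 2, 3 and 4. With baseline-to-post correlation ρ, adjusting for category instead of the continuous value multiplies residual variance by (1 − ρ²R²)/(1 − ρ²):

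| ρ (assumed) | K = 2 | K = 3 | K = 4 |
|---|---|---|---|
| 0.5 | 1.12 | 1.07 | 1.05 |
| 0.8 | 1.65 | 1.37 | 1.25 |
| 0.9 | 2.55 | 1.88 | 1.59 |

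These figures concern walking speed. A speed category is not an adjustment for baseline clearance, the other primary outcome.

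**6. Does baseline imbalance matter here?** The difference in mean baseline between two arms of six has standard deviation √(2/6) = 0.577 SD. Under normality, P(|difference| > 0.5 SD) = 2 × (1 − Φ(0.5/0.577)) = 39%.

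**The case against.** The strongest reply is that the protocol never states one-to-one pairing or the removal of unmatched subjects. That stands. A reader might infer that subjects will be left out, but the text does not say so, and steps 1 to 4 apply only if that is the meaning.

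A reader might also infer that matching will nearly always fail. The documents do not support this, because they do not give the number of categories. With two categories and arms held at six each, matching is incomplete in 58% to 77% of trials. The stronger phrase fits three or more categories, or independent tosses.

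A third inference, that bands from a stroke classification are wrong for MS, is not shown by anything in the documents. Nor is silence about the pairing procedure evidence of choices made after seeing the data; it is a gap in specification.

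The sentence could mean that pairs of similar speed were formed before the toss, since item 31 has eligibility assessed with "standard clinical 10 m and 6 minute walking tests". The words about data analysis and the plain coin toss in item 14 point the other way, and if pairing was intended, items 13 and 14 still need reconciling.

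Finally, the main contrasts (CVN−VGB and VGP−VGB) use each subject's own measured baseline, and item 10 presents the control comparison as a search for trends. That also stands and limits the reach of the point.

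**Conclusion.** The point holds in a limited form. The plan promises a matching step that it does not define and that appears in neither analysis section, after an allocation that was not described as arranged to support it. Read as one-to-one matching with six per arm and 2 to 4 equal categories, it can be completed in about 23%, 7% or 2% of trials and leaves about 3 to 5 of 12 subjects without a partner; independent tosses make this worse. Read as looser grouping, it loses nobody but discards about 36%, 21% or 14% of the variance in baseline speed and leaves baseline clearance unaddressed. The size depends on the assumed number and balance of categories and, for precision, on the assumed correlation. Only the exploratory comparison between arms is affected. It would be wrong to read this as a flaw in the within-subject contrasts.

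**What to change.** In Protocol item 13, delete the matching clause. In item 10 and the SAP, define the between-arm comparison as change in volitional gait from baseline to post-training (VGP−VGB), one mean value per subject, in all randomised subjects with data, with arm as the factor and the continuous baseline value of the same measure as covariate: baseline 10 m speed for speed, baseline clearance for clearance. Keep the walking category to describe the sample.

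This uses values already collected and requires wording changes only. It costs one degree of freedom: with 12 subjects the residual degrees of freedom fall from 10 to 9 and the two-sided 5% critical t rises from 2.228 to 2.262, with a small further loss of precision when the arms differ at baseline by chance. It also assumes a roughly linear relation with baseline, which 12 subjects can check only crudely.

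The SAP is written in the past tense. If the analysis has been done, report this as the between-arm analysis and label it as a change to the plan.

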Statistical Analysis Plan

Study Title: Cyclical muscle vibration in multiple sclerosis to improve walking

Last update: 01/29/2020

The within subject experimental design was used for this feasibility study because it requires fewer subjects with more statistical power while reducing the potential for systemic error or selection bias to test the effect of training with vibration on walking. While practice and carryover effects are major disadvantages of this study design, proper precautions including rest periods between tests and randomization of testing order for walking with or without vibration was instituted to minimize them at baseline and post-treatment¹. In this study design, any improvements at baseline with vibration compared to volitional gait can be attributed to short term effects of vibration. Improvements in volitional gait *post* training with vibration compared to volitional baseline gait can be attributed to long term effects of vibration. While this feasibility study design has limited generalizability due to the small number of subjects and inhomogeneity of the selected population, it can be quite useful for developing and refining future vibration intervention studies.

Means and standard deviations were calculated for all outcome measures for each subject. Differences in means were determined via a two-way analysis of variance ($p < 0.05$). A statistical power of 90% was used to determine the number of trials with VICON motion analysis system required for the testing and comparison of gait parameters. The results indicated a requirement of 30 strides of data or roughly 6 trials (approximately 5 strides per trial) for each condition (volitional or with vibration).

¹ Greenwald AG. With-in subject design: to use or not to use? *Psychological Bulletin*, 83(2):314-320, 1976.

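### The immediate effect of vibration is fully measured at baseline, but the planned repeated measures ANOVA, if fitted to complete cases, would discard it for treated subjects who leave before the post-training assessment

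*Protocol*

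**What the plan says.** Protocol Section 3, item 10 defines the short-term effect from two baseline measurements: "any improvements at baseline with CVN compared to volitional gait (VGB) can be attributed to short term effects of vibration". Item 13 (Recruitment and baseline evaluation) restricts that pair to one arm: "The baseline evaluation will be done with and without vibration on treatment group and without vibration on control group". Item 11 sets the arm's size: "a small sample of 6 subjects were chosen for intervention with six controls to obtain preliminary data".

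For the analysis, item 10 states: "A one-way repeated measures ANOVA will be used to test for significant difference between means to test Hypotheses 1 and 2". Tukey comparisons then cover "statistically significant differences between conditions (CVN-VGB, CVN-VGP, VGP-VGB"), so the conditions in the model are VGB, CVN and VGP. The last of these exists only after twelve training sessions.

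The SAP has a different model: "Differences in means were determined via a two-way analysis of variance ($p < 0.05$). It does not name the two factors, mention the control group or say how incomplete subjects are handled. Section 4, item 20 plans to screen up to 48 people to reach 12 completers. Section 8, item 65 lists several reasons for removing a subject, including worsening, intolerable complications and withdrawal. Neither document says what happens to the baseline data of someone who leaves.

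**The concern.** CVN minus VGB needs nothing that happens after the baseline visit. Placing it in a model with VGP ties it to a later measurement that it does not use. The classical repeated measures ANOVA works on subjects with a value in every condition, so a treated subject who leaves during training would also drop out of a contrast already fully observed.

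Two things are at stake. The first is precision: item 11 says the study exists to obtain an effect size for planning a larger trial, and with about six subjects each pair counts. The second is selection: several removal grounds in item 65 could be related to how a subject responds to vibration, in which case completers are a selected group for the immediate effect. The documents give no basis for putting a size on that second risk.

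**Working it through.** **The plan's own figure.** Items 11 and 13 and the SAP give 6 trials × about 5 strides = 30 strides per condition, which agrees. The 90% power behind it concerns the number of trials. It cannot be checked, because no effect size or SD is given. More strides reduce within-subject noise but do not replace a lost subject.

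**Inputs.**
- Treated subjects: 6 (items 11 and 13).
- Level: 0.05 (item 10, SAP). Two-sided is my assumption, as sidedness is not stated.
- SD of the paired difference CVN − VGB: not given. All results are in units of this SD, taken as equal for completers and dropouts.
- Dropout: no rate given. The numbers below are illustrative.

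**Paired 95% half-width** = t(0.975, n−1)/√n.

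| Pairs analysed | Situation | Calculation | Half-width |
|---|---|---|---|
| 6 | all treated pairs kept | 2.571/√6 | 1.05 |
| 5 | one dropout excluded, not replaced | 2.776/√5 | 1.24 |
| 4 | two excluded, not replaced | 3.182/√4 | 1.59 |
| 7 | six completers plus one retained dropout pair | 2.447/√7 | 0.92 |
| 8 | six completers plus two retained dropout pairs | 2.365/√8 | 0.84 |

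Relative to six pairs, losing one widens the interval by 18% (1.242/1.049) and losing two by 52% (1.591/1.049). Where dropouts are replaced, retaining one or two extra pairs narrows it by 12% (0.925/1.049) or 20% (0.836/1.049).

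**The planned Tukey interval.** With three conditions, pooled error on 2(n−1) degrees of freedom and equal SDs for all pairwise differences, the half-width is q(0.95; 3, 2(n−1))/√(2n):
- n = 6: 3.88/√12 = 1.12
- n = 5: 4.04/√10 = 1.28
- n = 4: 4.34/√8 = 1.53

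The pattern is the same. The paired interval on all six is narrower than each of these, partly because it carries no adjustment for three comparisons.

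**How likely a loss is.** With independent dropout at an assumed rate p, the chance that all six treated subjects complete is (1−p)^6, and 6(1−p) complete on average:
- p = 10%: 53%, 5.4 complete
- p = 20%: 26%, 4.8 complete
- p = 30%: 12%, 4.2 complete

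**Arm size.** Item 14 says: "Subjects will be randomly assigned to either treatment or control group using a coin toss". With 12 uncapped tosses, exactly 6:6 occurs with probability 924/4096 = 22.6%, so six is the target and not a certainty.

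**The case against.** The strongest reply is that no exclusion is written anywhere. Item 10 lists CVN−VGB as its own pairwise contrast, the SAP names another model, and an analyst could fit either so as to keep incomplete subjects. This stands: the point concerns what the named method does in its classical form and a gap in the text. A reader might infer that the plan requires treated subjects to complete training before they count for the immediate effect. The documents do not say so.

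Second, item 20 counts completers. If dropouts are replaced, six complete treated subjects remain and the five- and four-pair rows do not arise. This also stands. In that case, however, complete-case analysis discards the additional pairs that would bring the half-width to 0.92 or 0.84.

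Third, the assessment after training also includes walking with vibration (item 13, Gait evaluation after gait training). This gives treated completers a second pair. It measures the immediate effect in trained subjects, whereas item 10 defines the effect at baseline, and it does not exist for those who leave.

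Finally, this is a feasibility study with no power target for subjects, so no stated requirement is missed. That is true and limits the weight of the point. Precision is still what the study is meant to deliver.

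**Conclusion.** The point holds as a gap in the analysis plan. The immediate effect is observed in full at baseline in the treatment group, but the protocol's named model can lose it for reasons unrelated to its measurement. If one or two of six treated subjects leave, are excluded and are not replaced, the 95% half-width grows from 1.05 to 1.24 or 1.59 SD. If they are replaced, the loss is the difference between 1.05 and 0.92 or 0.84. These figures rest on an unstated SD, illustrative dropout and the 6:6 target. With no dropout there is no loss of pairs.

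A tempting stronger reading is that half the sample is wasted because controls could supply the same pair once their last volitional walk is recorded. Twelve pairs would give a half-width of 0.64 (2.201/√12). The documents do not support counting that as available precision. Item 10 limits controls to volitional gait: "The control group subjects will be evaluated at baseline (VGB) and after gait training (VGP). A control pair would be taken after twelve training sessions, only in completers, and with volitional walking always first, whereas the SAP randomises the order of walking with and without vibration. Arm, training state and order would coincide. An order or fatigue bias of b SD in six of twelve equally weighted pairs moves the pooled mean by 6b/12 = b/2, and a term for arm cannot separate it from the effect. Such walks could at most be a separately reported exploratory measure.

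**What to change.** State in the SAP that CVN minus VGB is estimated by a paired comparison of all treated subjects with both baseline values, whether or not they complete training, with its 95% interval and the number of pairs. Keep the contrasts involving VGP for subjects with VGP. A mixed model that retains incomplete subjects would be an acceptable alternative.

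The SAP should also:
- say whether dropouts are replaced, and that a replaced subject's baseline pair is still used;
- name the factors of the two-way ANOVA and reconcile it with the protocol's one-way model;
- say whether CVN−VGB is still adjusted for multiple comparisons once it leaves the Tukey family.

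The cost is SAP wording, with no new visit, procedure or data. The SAP is written in the past tense, so the analysis may already have been run. If so, the paired analysis can be added from existing data and labelled as added later.
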